## **10.0 Provisions to Protect the Privacy Interests of Subjects**

*Before completing this section, refer to the special instructions below about use of study participants' health information.*

*10.1 Describe the steps that will be taken to protect subjects' privacy interests.*  
*"Privacy interest" refers to a person's desire to place limits on whom they interact or whom they provide personal information.*

The importance of confidentiality within the group will be emphasized, as will the importance of attending the sessions from a private location, preferably with headphones. Participants will not be required to share private information in the group setting. On the surveys, they will be encouraged to answer all questions.

*10.2 Describe what steps you will take to make the subjects feel at ease with the research situation in terms of the questions being asked and the procedures being performed. "At ease" does not refer to physical discomfort, but the sense of intrusiveness a subject might experience in response to questions, examinations, and procedures.*

We have built in "ice breaker" activities that encourage participants to get to know and become comfortable with other group members. We will stress the importance of confidentiality throughout the intervention process.

*10.3 Indicate how the research team is permitted to access any sources of information about the subjects.*

Research team will have access via the data set stored on the OneDrive password protected file, as described above.

## **11.0 Compensation for Research-Related Injury**

*This section is required for any study that may involve: (1) any harm or discomfort for which the probability or magnitude is greater than those that may be ordinarily encountered by healthy persons in daily life or during the performance of routine physical or psychological examinations or test; (2) a clinical trial; (3) a FDA-regulated product(s) (e.g., drugs, devices, biologics, nutritional supplements or combination products); and/or (4) is funded by any federal department or agency:*

*11.1 Describe what specific arrangements and referrals will be made in the event a subject experiences a research related injury.*

Any injury resulting from participation in this study will be reported to the Institutional Review Board and funding agency (if applicable).

*11.2 Describe the available compensation in the event of research related injury.*

The Institution has no policy or plan to pay for any injuries that you might receive as a result of participating in this research protocol.

## **12.0 Consent Process**

*12.1 Indicate whether you will you be obtaining consent, and if so describe:*

- *Where will the consent process take place*
  - Online/electronically
- *Any waiting period available between informing the prospective subject and obtaining the consent.*
  - No
- *Any process to ensure ongoing consent.*
  - Consent is provided for the length of the intervention only, no follow up is needed.
- *Whether you will be following "SOP: Informed Consent Process for Research (HRP-090)." If not, describe:*
  - *The role of the individuals listed in the application as being involved in the consent process.*
    - a. *Either [name], [name], or [name] may be involved in the consent process of meeting with parents or assent process for meeting with children. The meeting will take place via Zoom.*
  - *The time that will be devoted to the consent discussion.*
    - a. *15 minutes*

- *Steps that will be taken to minimize the possibility of coercion or undue influence.*
  - a. *It is clear in writing that they are not required to participate and choosing to do so will not impact their relationship with us or FSU.*
- *Steps that will be taken to ensure the subjects' understanding.*
  - a. *The consent and assent forms are written in simple jargon free language.*
  - b. *A zoom meeting will be held to answer any questions they might have.*

## 13.0 Process to Document Consent in Writing

13.1 *Describe whether you will be following "SOP: Written Documentation of Consent (HRP-091)." If not, describe whether and how consent of the subject will be documented in writing.*

We request that the written documentation be completed electronically via DocuSign. The parent will sign the form electronically, then it will be sent to [name] to sign. DocuSign will automatically send the completed form with both signatures to both parties (parents and [name]). [name] will download all completed consent forms and store them in a OneDrive folder. Only [name] and project staff have access to the OneDrive folder.

13.2 *If your research presents no more than minimal risk of harm to subjects and involves no procedures for which written documentation of consent is normally required outside of the research context, the IRB will generally waive the requirement to obtain written documentation of consent.*

13.3 *(If you will document consent in writing, attach a consent document. If you will obtain consent, but not document consent in writing, attach a consent script. Review "CHECKLIST: Waiver of Written Documentation of Consent (HRP-411)" to ensure that you have provided sufficient information. You may use "TEMPLATE CONSENT DOCUMENT (HRP-502)" to create the consent document or script.)*

Consent and assent forms are attached, but the text will be put into Qualtrics.

## 14.0 Setting

14.1 *Describe the sites or locations where your research team will conduct the research.*

- *Identify where your research team will identify and recruit potential subjects.*

Local Tallahassee social media groups (e.g., Tally Moms) and local schools.

- *Identify where research procedures will be performed.*

All research will be performed virtually. The intervention will be delivered virtually via HIPPA-compliant Zoom meetings.

## 15.0 Resources Available

### 15.1 Describe the resources available to conduct the research: For example, as appropriate:

- *Justify the feasibility of recruiting the required number of suitable subjects within the agreed recruitment period. For example, how many potential subjects do you have access to? What percentage of those potential subjects do you need to recruit?*

Using online recruiting makes it difficult to ascertain the number of potential subjects; however, reaching parents directly via social media or through schools makes it feasible to obtain the number of youth needed for the study. Exact size of the potential subject pool is difficult to ascertain.

- *Describe the time that you will devote to conducting and completing the research.*

The PI is dedicating approximately 4 hours per week to this project. The GAs are dedicating 10 hours (foundation-funded project) or 20 hours (NIH-funded project) each per week. There is also a research post doc, [name], who is dedicating 15 hours per week to the project. [name]'s start date is January 2024.

- *Describe your facilities.*

Project staff will use their personal or FSU provided laptops, Qualtrics and Zoom are free from FSU. The project is funded through a foundation grant.

- *Describe the availability of medical or psychological resources that subjects might need as a result of an anticipated consequences of the human research.*

The PI is a licensed psychologist and is available to assist if needed. If the PI feels that the participant would benefit from individual counseling, referrals to free and fee-based counseling will be made. There will also be a list of mental health resources provided to all participants (See attached "mental health resources" document).

- *Describe your process to ensure that all persons assisting with the research are adequately informed about the protocol, the research procedures, and their duties and functions.*

The GAs and post doc will involved in refining the intervention, therefore are inherently familiar with the protocol. They have completed the CITI training and also have general counseling training from their doctoral program as well.

Official Title: IVY: Intervention for Victimized Youth

NCT Number: NCT06631274

Document Date: October 18, 2024

Analytic Plan

Analytic Plan

Statistical analyses included three steps. First, missing data occurred only on items measuring social support. Little's test was used to examine the tenability of the assumption of missing completely at random. Second, the mean scores across items in each scale/subscale were computed to represent each intermediate and distal outcome. Third, a series of one-way repeated measures ANOVAs was conducted to examine the impact of intervention, in which participation in the intervention (treatment vs. control) was used as the between-subject factor and time points (time 1 and time 2) was used as the within-subject factor. In addition to significance test for main effect of group, main effect of time, and the interaction effect between time and group, Hedges' g was computed to indicate effect size, where values of 0.2, 0.5, and 0.8 indicate a small, medium, and large effect respectively.

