## **1.0 Procedures Involved**

### *1.1 Describe and explain the study design.*

The study uses a quasi-experimental design with a waitlist control. Youth will be recruited and randomly assigned to either the experimental group or the waitlist control group. At the completion of the experimental group, the waitlist control group will start.

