### *1.2 Provide a description of all research procedures being performed and when they are performed, including procedures being performed to monitor subjects for safety or minimize risks.*

Students will take pre-tests before participating in an 8-week small group therapy. Afterwards, post-tests will be administered and students will be given a chance to provide feedback. A list of the measures is below.

Recruitment will occur by advertising via social media outlets (e.g., Facebook groups targeting local moms) and through local schools. The graphic in the file titled “participants needed” will be posted on social media.

An online survey will be shared with interested caregivers to gauge eligibility. Caregivers will first provide parental consent for their child’s participation, then an eligibility questionnaire will be administered electronically. To be eligible for the study, their child must 1) be a middle or high school student (via caregiver report), 2) have access to a computer with webcam and a private space for each meeting (via caregiver report), and 3) have experienced at least one instance of peer victimization in the past month. The goal is to enroll 6-7 students in the group. Once the group has been enrolled, student assent will be gathered and pre-test surveys will be administered. Participants completing the intervention will be asked to complete the post-test surveys and will be invited to be part of the focus group to gather their feedback.

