**2.0 Study Timelines**

**2.1 Describe:**

- *The duration of an individual subject's participation in the study.*

*10 weeks. One week of data collection before and after the 8 week intervention.*

- *The duration anticipated to enroll all study subjects.*

*Enrollment for the foundation-funded project will occur during September 2023-April 2024.*

*Enrollment for the NIH-funded project will occur during August 2024-May 2025.*

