## **8.0 Data Management and Confidentiality**

### *8.1 Describe the data analysis plan, including any statistical procedures or power analysis.*

An initial indication of changes in the outcome variables will be explored. A repeated measures ANOVA will be used to assess change in pre- and post- outcome measures. The small sample size may limit the power to detect statistically significant differences (Thompson, 1996; Valentine & Cooper, 2003); thus, effect sizes will also be calculated. Based on a large meta-analysis of over 800 meta-analyses in education, Hattie (2009) categorized a small effect as .20, medium as .40, and large effect as .60. If there is missing data (e.g., a participant dropped out), scores will be deleted list-wise.

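### Little's test, the SAP's only check on missing social support items, could not justify the protocol's list-wise deletion; use a mixed model and state the scoring rule

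*SAP*

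**What the plan says.** **SAP, Analytic Plan.** The first step states that "missing data occurred only on items measuring social support" and that "Little's test was used to examine the tenability of the assumption of missing completely at random". It gives no test result, significance level, list of variables entered, amount of missingness, or action for either outcome of the test. In the second step, "the mean scores across items in each scale/subscale were computed to represent each intermediate and distal outcome"; whether a mean is formed when some items are blank is not said. The third step is a repeated measures ANOVA with group and two time points, which needs a score at both.

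**Protocol 8.1.** This holds the only rule for missing scores in either document: "If there is missing data (e.g., a participant dropped out), scores will be deleted list-wise". Dropout is an example; the rule itself is general. The same section warns that "The small sample size may limit the power to detect statistically significant differences". Sections 5.2 and 5.3 separately delete the data of terminated and withdrawn participants.

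**Size.** Protocol 1.2 says "The goal is to enroll 6-7 students in the group", and 1.1 says "Youth will be recruited and randomly assigned to either the experimental group or the waitlist control group". The number of groups and the total N are not stated. Section 2.1 lists two enrolment periods, the second being "Enrollment for the NIH-funded project will occur during August 2024-May 2025".

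**Measure.** Social support is not among the four pre/post measures named in Protocol 1.3, so its handling could only be found in the SAP.

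**The concern.** Missing completely at random (MCAR) is the null hypothesis of Little's test. Using the test to judge whether MCAR is tenable invites the reader to take a non-significant p-value as support for it. In a small sample that p-value says little, and the protocol's own warning about power applies to this test as well. The test also sees missingness only through the variables entered into it.

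List-wise deletion is guaranteed to be unbiased in general only under MCAR. If a non-significant test were cited in its favour, youths with incomplete support scores could be left out of that outcome with no sound ground for calling the omission harmless. The cost would be lost precision and, under the condition worked out below, a biased time-by-group effect.

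**Working it through.** **Plan's own figure.** There is none to reproduce: neither document gives a total N, a power or a significance level for this test.

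**Inputs**
- From the documents: 6-7 youths per group; two arms.
- Assumed: one or two groups per arm, so N is 12-14 or 24-28, with N = 60 and 100 shown in case both enrolment periods are pooled. Two-sided alpha is 0.05. Between 10% and 30% of youths have a missing support score. Complete and incomplete youths differ by d = 0.5, 0.8 or 1.0 SD on one fully observed scale.

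**Step 1: power.** With two missingness patterns and one fully observed scale, Little's test is approximately a comparison of that scale's mean between incomplete (n_m) and complete (n_c) youths:

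z = d / sqrt(1/n_m + 1/n_c), and power = Φ(z − 1.96) + Φ(−z − 1.96).

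Example, N = 28 with 30% incomplete (n_m = 8, n_c = 20): z = 0.5 / sqrt(1/8 + 1/20) = 0.5 / 0.418 = 1.195. Power = Φ(−0.765) + Φ(−3.155) = 0.222 + 0.001 = 0.223.

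Power at 0.5 SD, with n_m rounded to whole youths:

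| N | 10% incomplete | 20% | 30% |
|---|---|---|---|
| 12 | 0.077 | 0.099 | 0.129 |
| 14 | 0.077 | 0.120 | 0.135 |
| 24 | 0.104 | 0.169 | 0.200 |
| 28 | 0.130 | 0.192 | 0.223 |
| 60 | 0.213 | 0.341 | 0.427 |
| 100 | 0.323 | 0.516 | 0.630 |

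Over N = 12-28 the miss rate runs from 1 − 0.223 = 78% to 1 − 0.077 = 92%. For 0.8 SD over the same N, power is 12-48%; for 1.0 SD it is 16-67%. Total N for 80% power is 150-349 at 0.5 SD, 59-137 at 0.8 SD and 39-88 at 1.0 SD.

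**Step 2: check by simulation.** Little's statistic was simulated directly (4,000 runs per setting). With a 0.5 SD shift, one scale and 15% or 30% incomplete, it rejected in 8% or 11% of runs at N = 14 and in 14% or 21% at N = 28, in line with the table. Entering four scales lowered this to 2% at N = 14 and 7-8% at N = 28.

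**Step 3: missingness driven by the unseen value.** Missingness was made to depend only on the support value itself (20% incomplete, log-odds slope 0.8 per SD).
- When support was unrelated to the other variables in the test, rejection stayed at about 2-5% for every N from 14 to 100, no more than the false-positive rate. The complete-case mean was off by about 0.14-0.15 SD.
- When one entered variable correlated 0.5 with support, rejection rose, but only to 7% at N = 14, 10.5% at N = 28 and 30.5% at N = 100.

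**Step 4: when deletion biases time-by-group.** In arm a, let π_a be the share omitted, R_a the mean change in retained youths and O_a the mean change in omitted youths. The true mean change is (1 − π_a)R_a + π_a·O_a, so list-wise deletion is off by π_a(R_a − O_a). The interaction is off by

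π_T(R_T − O_T) − π_C(R_C − O_C).

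If omitted youths differ only by a stable level, R_a = O_a and the bias is zero, even with unequal shares omitted. If their change differs by 0.5 SD in both arms, with 30% omitted in one arm and 10% in the other, the bias is 0.30 × 0.5 − 0.10 × 0.5 = 0.10 SD. These values are illustrative only.

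**The case against.** A reader might infer that Little's test came out non-significant, that MCAR was accepted and that the affected youths were dropped. The documents do not say so. The SAP reports no result and no deletion. The missingness is on items and the outcome is an item mean, so answered items may already have been averaged and few or no youths lost. That stands. It turns the point into a rule in 8.1 that lacks justification plus an omission in the SAP, rather than a demonstrated loss of participants. If answered items were averaged, the SAP departs from 8.1 without saying so, and the two still need reconciling.

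A reader might also take the low power as a property of the trial's actual size. That size is not documented, and pooling two enrolment periods could make it larger. At N = 60 with 20-30% incomplete, a 0.8 SD difference is detected 70-81% of the time. Even at N = 28 with 30% incomplete, a 1.0 SD difference is found 67% of the time. In addition, the calculation treats the whole support score as missing; answered support items entered into the test could carry some signal about the skipped ones. These limits stand for the power figures. A larger N does not by itself remove the problem in step 3.

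Finally, a difference in level between omitted and retained youths does not bias the interaction; a difference in change is needed. That is correct, and the stakes are stated on that basis.

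**Conclusion.** The point holds in limited form. Protocol 8.1 prescribes list-wise deletion, the SAP acknowledges missing social support items, and the only support offered for MCAR is a test that could not supply it. Under the assumed N of 12-28 and 10-30% incomplete, the test misses about 78-92% of 0.5 SD differences on one observed scale. It is blind at any N to missingness that depends only on the unseen support value, unless another entered variable carries that signal. Bias in the time-by-group effect is possible but not shown: its size depends on how much omitted youths' change differs and on the share omitted per arm, neither of which is reported. The scope is the social support outcome, among youths whose data are retained; data deleted under 5.2 and 5.3 are outside the reach of both the test and the fix below.

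**What to change.** 1. In the SAP, do not use Little's test to justify deletion, whatever its p-value. If it is reported, give the result and the variables entered, and say that non-significance does not establish MCAR.
2. For social support, replace the list-wise rule with a likelihood-based mixed model (arm, time, arm-by-time) on all available scores, so that a youth with a score at only one time point still contributes. With complete data and suitable small-sample degrees of freedom it gives the planned interaction test. Show the list-wise result as a sensitivity analysis.
3. State the scoring rule for partly answered scales: for example, the mean of answered items when at least half are answered, or item-level multiple imputation. Item-mean scoring assumes that the answered items represent the scale, and it can be biased even under MCAR. With four items whose means are 2, 2, 2 and 4, the scale mean is 2.5; if the last is missing at random for 20% of youths, the sample mean becomes 0.8 × 2.5 + 0.2 × 2.0 = 2.4.
4. Report the total N and the missing social support data by arm and time point.
5. Amend 8.1 to match.

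The cost is some text and a few lines of code, with no new data. The downside is that the mixed model relies on missing at random. Neither it nor the list-wise comparison protects against missingness driven by the unseen support value, and the SAP should say so.

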### 5.2 *Describe any procedures for orderly termination.*

If subjects are terminated, their data will be deleted and they will not be included in the planned analysis.

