### 5.3 *Describe procedures that will be followed when subjects withdraw from the research, including partial withdrawal from procedures with continued data collection.*

If subjects wish to withdraw, their data will be deleted and they will not be included in the planned analysis.

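### The SAP groups youths by participation, and neither document commits to analysing them in the arm to which they were randomised

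*SAP*

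**What the plan says.** Protocol section 1.1 sets up a randomised comparison: "Youth will be recruited and randomly assigned to either the experimental group or the waitlist control group". The waitlist receives IVY later: "At the completion of the experimental group, the waitlist control group will start".

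The SAP's Analytic Plan has one group variable: "participation in the intervention (treatment vs. control) was used as the between-subject factor". It does not mention randomisation, assignment, intention-to-treat or an analysis set. The protocol has no analyse-as-randomised statement either.

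Four protocol rules decide who can reach the analysis:

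- Section 1.2, on who is asked for outcomes: "Participants completing the intervention will be asked to complete the post-test surveys".
- Section 5.2, on termination: "If subjects are terminated, their data will be deleted and they will not be included in the planned analysis".
- Section 5.3, on withdrawal: "If subjects wish to withdraw, their data will be deleted and they will not be included in the planned analysis".
- Section 8.1, on dropout: "If there is missing data (e.g., a participant dropped out), scores will be deleted list-wise".

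On incompleteness, the SAP reports that "missing data occurred only on items measuring social support".

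**The concern.** Assignment and participation are different variables. Assignment is fixed by chance before anything happens; participation is partly the youth's or family's choice, and partly the result of how the sessions go. Groups formed by participation need not be comparable at baseline or in prognosis, even when the trial was randomised.

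The SAP's factor defines the time-by-group interaction and is the natural grouping for Hedges' g, so it determines what the main result means. If youths who do not take up or stay in the group differ in distress or expected course from those who do, and they are lost mainly from the IVY arm, the interaction estimates a mixture of IVY's effect and selection. A reader of the results could not tell which.

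**Working it through.** **Reading the passages together.** Neither document states a sample size, power or alpha, so there is no planned figure to reproduce. Consider a youth randomised to IVY who attends few or no sessions.

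1. Under section 1.2 as worded, the post-test request goes to those who complete the intervention, so this youth may not be asked for one. Section 4.1 ties payment to at least 6 of 8 sessions and pays nothing for partial completion, which weakens the incentive to return it.
2. If the youth withdraws or is terminated, sections 5.2 and 5.3 delete the data. Section 5.3 does not separate stopping the sessions from withdrawing from data collection.
3. If the youth simply drops out, section 8.1 removes the case.
4. If the youth does supply both scores, the SAP's factor, taken literally, does not place a non-participant in the treatment group.

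No step keeps this youth in the IVY arm by rule. Section 5.1 also allows a participant to be asked to discontinue because of distress over the topic. Until the waitlist group starts, distress caused by sessions can arise only in the IVY arm, so this route to deletion is not obviously balanced.

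**Illustration of size.** From the documents: a target of 6 to 7 youths in the group (section 1.2) and 0.2 as a small effect (SAP). Assumed: equal arms of n; no true effect of IVY; k youths in each arm who would not stay in a therapy group; mean change in those youths differing from the others' by d SD; removal from the IVY arm only.

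- Set the other youths' mean change to 0. Each full arm then has mean change −kd/n, and the as-randomised difference is 0 for any n, k and d.
- Remove the k youths from the IVY arm. Its mean becomes 0, the waitlist mean stays at −kd/n, and the spurious difference is kd/n.

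With k = 1:

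| n per arm | one youth as share of arm | d = 0.5 | d = 1.0 |
|---|---|---|---|
| 6 | 1/6 = 17% | 0.5/6 = 0.08 | 1/6 = 0.17 |
| 7 | 1/7 = 14% | 0.5/7 = 0.07 | 1/7 = 0.14 |
| 28 (assumed) | 1/28 = 4% | 0.5/28 = 0.02 | 1/28 = 0.04 |

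If the same kind of youth is also removed from the waitlist, both means become 0 and the spurious difference disappears. If those who leave would have changed for the better rather than the worse, the sign reverses.

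**The case against.** The strongest reply is that the SAP uses participation as a name for the arm. It labels the two levels as treatment and control and then speaks of group effects. In a waitlist design where controls start only after the first group ends, taking part between time 1 and time 2 can simply describe assignment. That reading is possible and nothing rules it out. It cannot safely be presumed, because no sentence in either document confirms it and section 1.1 itself calls the randomised design quasi-experimental.

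A second reply is that renaming the factor would not recover a youth whose data were deleted or who has no time 2 score. That is right, and it is why the fix must also reach the post-test and deletion rules.

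A third is that those rules apply to both arms, that section 8.2 lists measures to limit attrition, and that the SAP reports little missing data. The first two limit the likely size. The third fits a file of completers as well as it fits full retention, and proves neither.

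A reader might infer more than the documents support:

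- *That non-attenders are counted as controls.* No passage reclassifies anyone; the stated rules remove such youths. The shift on that route would be 2kd/(n+k), or 0.13 to 0.29 SD for one youth at 6 to 7 per arm, but it should not be put forward as what the plan does.
- *That youths are moved to the later group.* No passage provides for or reports a move.
- *That the error favours IVY.* The direction depends on who leaves, and the documents do not say.

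**Conclusion.** The plan does not commit to comparing the randomised groups, and followed literally it can fail to do so. That goes beyond missing detail, because the participation factor, the post-test wording and the deletion rules all act the same way. It is not shown that the analysis departed from randomisation.

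The size is unknown. In the illustration, one lost youth at the stated group size approaches but does not reach the 0.2 that the SAP calls small, and at 28 per arm the shift is negligible. These figures rest on assumed equal arms, an assumed difference of 0.5 to 1.0 SD, one such youth and one-sided removal. Comparison with 0.2 is approximate, since the SAP does not say which SD standardises Hedges' g. This is a should-fix.

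**What to change.** **SAP.** Define the between-subject factor as randomised assignment (IVY vs. waitlist). State that every youth with outcome data is analysed in the assigned arm, whatever the number of sessions attended. Present any participation-based analysis, for example at least 6 of 8 sessions, as secondary only.

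**Protocol.** In section 1.2, ask every randomised youth in both arms for the post-test, whether or not the sessions were completed. In sections 5.2 and 5.3, keep data already collected from youths who stop sessions or are terminated, unless the family asks for deletion.

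**Reporting.** Give the numbers randomised, started, stopped and analysed in each arm. The SAP is written in the past tense, so for data already collected these counts may be the main remedy still available.

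**Cost.** A sentence or two in the SAP, short protocol edits, a few more post-test requests and, if participation was the variable used, one rerun. If assignment was used, the SAP need only say so and no rerun on the factor is needed. The downside is that the estimate may be slightly smaller, because youths who attended little stay in the IVY arm.

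### The SAP lists group, time and interaction tests without naming the one that estimates the intervention effect, and Hedges' g has no contrast, no standardiser and two conflicting sets of cut-offs

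*SAP*

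**What the plan says.** The SAP (Analytic Plan) states that "a series of one-way repeated measures ANOVAs was conducted to examine the impact of intervention", with arm as the between-subject factor and Time 1 and Time 2 as the within-subject factor. It then lists, on equal footing, a "significance test for main effect of group, main effect of time, and the interaction effect between time and group". On effect size it says only that Hedges' "g was computed to indicate effect size, where values of 0.2, 0.5, and 0.8 indicate a small, medium, and large effect respectively". Time 1 is a level of the within-subject factor; no covariate is named.

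Protocol section 8.1 adds little: "A repeated measures ANOVA will be used to assess change in pre- and post- outcome measures". It warns that the small sample may limit power, "thus, effect sizes will also be calculated", and cites a source that "categorized a small effect as .20, medium as .40, and large effect as .60". It gives no contrast or standard deviation either.

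On design, protocol section 1.1 says "Youth will be recruited and randomly assigned to either the experimental group or the waitlist control group", yet labels the design quasi-experimental in the same paragraph.

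**The concern.** The stated purpose is to measure the impact of the intervention, but two of the three listed tests do not estimate it. A plan that names no deciding test leaves that choice to whoever reports the results.

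The gap in g matters more than it usually would. Section 8.1 expects limited power and turns to effect sizes for that reason, so the reading of the trial will lean on g. The same data can earn different size labels depending on which difference is standardised, by which standard deviation, and against which document's cut-offs.

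**Working it through.** **Inputs.** The documents state no power, alpha, total sample size, pre-post correlation r or expected effect, so there is no planned figure to reproduce. Protocol section 1.2 aims for 6-7 students in the group; I take this as per arm, which is an assumption. Other assumptions: equal arms, independent participants, normal scores with SD 1 at both times, two-sided 0.05, true Time 2 effect d = 0.8 SD, r = 0.5 or 0.8, no common change unless stated, and both control assessments made before the control arm's own group starts. Simulated results use 60,000 replicates per setting.

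**Step 1: what each test estimates.** Let c be the change common to both arms. With two time points and equal arms:
- Interaction: between-arm difference in mean change, expectation d. Its F is the squared t statistic on change scores (checked by a full sum-of-squares decomposition on a simulated data set: 0.0586 both ways).
- Group effect: between-arm difference in the average of Time 1 and Time 2, expectation d/2 (F 2.446 both ways).
- Time effect: average change over both arms, expectation c + d/2.

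Time 1 enters all three tests. Adding 1 SD to Time 1 in the treated arm of that data set moved the F values from 2.45 to 7.33 (group), 1.08 to 1.53 (time) and 0.06 to 4.13 (interaction).

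**Step 2: power at 7 per arm (12 degrees of freedom).** The variance per participant is 2(1−r) for change and (1+r)/2 for the average. The noncentrality is the expected difference divided by √(2 × variance / 7).

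| r | Interaction | Group effect |
|---|---|---|
| 0.5 | 0.8/√(2×1.0/7) = 1.50; power 28% | 0.4/√(2×0.75/7) = 0.86; power 12% |
| 0.8 | 0.8/√(2×0.4/7) = 2.37; power 58% | 0.4/√(2×0.9/7) = 0.79; power 11% |

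The two tests disagree on significance in 34% (r = 0.5) or 57% (r = 0.8) of trials. Most of that is the interaction being significant when the group effect is not. The group effect alone is significant in 9% or 5%.

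**Step 3: error if any of the three could count.** With no treatment effect and no common change, at least one is significant in about 14% of trials per outcome (1 − 0.95³ = 14.3% under independence). If both arms shift by 0.5 SD (r = 0.5), this rises to about 46%, because the time test picks up the shift.

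**Step 4: which g.** Values before small-sample correction:

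| Contrast and standardiser | Formula | d = 0.8; r = 0.5 / 0.8 | d = 0.5; r = 0.5 / 0.8 |
|---|---|---|---|
| Change difference, raw SD | d | 0.80 / 0.80 | 0.50 / 0.50 |
| Change difference, change-score SD | d/√(2(1−r)) | 0.80 / 1.26 | 0.50 / 0.79 |
| Group effect, its own SD | (d/2)/√((1+r)/2) | 0.46 / 0.42 | 0.29 / 0.26 |

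**Step 5: which cut-offs.** Reading cut-offs as lower bounds, 0.42 to 0.46 is small in the SAP and medium in the protocol. For the change difference over the Time 1 SD, the two sets label the same estimate differently in 22% (r = 0.5) or 30% (r = 0.8) of trials. Replacing the Time 1 SD by the Time 2 SD changes the SAP label in 21% or 19%, so the time point of the SD has to be named too. At r = 0.5 the 95% sampling range of this g is about −0.25 to 2.05.

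**Step 6: Time 1 as a covariate.** The variance of ANCOVA relative to the interaction is (1+r)/2 × [1 + 1/(N−4)], with N the total. For N = 14 this is 0.75 × 1.1 = 0.83 at r = 0.5, 0.90 × 1.1 = 0.99 at r = 0.8 and 0.95 × 1.1 = 1.05 at r = 0.9.

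| Power, ANCOVA vs interaction | r = 0.5 | r = 0.8 | r = 0.9 |
|---|---|---|---|
| 6 per arm | 28% vs 24% | 50% vs 51% | 76.4% vs 79.5% |
| 7 per arm | 33% vs 28% | 59% vs 58% | 85% vs 87% |
| 14 per arm (assumed) | 64% vs 53% | 91% vs 90% | – |

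**The case against.** The strongest reply is that this is a standard two-arm, two-time ANOVA. The three tests are its routine output, and any statistician would read the interaction. The SAP's reference to impact and the protocol's reference to change both point that way. That is fair, and it makes the first gap one missing sentence. It does not settle g: convention fixes neither its contrast nor its standard deviation, and the cut-off conflict stands however the tests are read.

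A reader might infer that the investigators mean to claim efficacy from any of the three tests, so that the error rate is 14% or more. Neither document says so; those figures show only what that reading would cost. Nor should the 34-57% disagreement be read as the chance of a spurious success: it mostly reflects the low power of the group effect.

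A reader might also infer that omitting Time 1 as a covariate makes the analysis invalid. Under random allocation the interaction is valid, and ANCOVA is a question of efficiency. At 6-7 per arm ANCOVA gains little or nothing at r = 0.8 and loses slightly at r = 0.9, so there is no case for putting it first.

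The arm size is uncertain as well. Protocol section 2.1 lists two funded enrolment periods, so there may be more than one group per arm. Members of a therapy group may also not be independent, as the figures assume.

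**Conclusion.** The point holds as a reporting and specification gap that should be closed. The plan offers three tests of the intervention's impact, of which only the interaction estimates it. It leaves g undefined while relying on it, and the two documents disagree on what counts as a medium or large effect. The algebra (d, d/2, c + d/2) and the cut-off conflict do not depend on assumed values. The sizes do: power of 28-58% against 11-12%, and different labels in about 22-30% of trials, rest on 7 independent participants per arm, a true effect of 0.8 SD and r between 0.5 and 0.8. The documents do not support a finding that the ANOVA is invalid or that a main effect was read as efficacy.

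**What to change.** 1. Name the time-by-group interaction as the test of the intervention effect for each outcome, and report the group and time main effects as descriptive only.
2. Define Hedges' g as the between-arm difference in mean change divided by the Time 1 SD pooled within arms, with the small-sample correction and a 95% confidence interval that allows for the pre-post correlation, for example by bootstrap.
3. Use one set of cut-offs in both documents.
4. Reconcile random assignment with the quasi-experimental label in protocol section 1.1. If allocation was random, add ANCOVA of Time 2 on arm plus Time 1 as a supporting analysis. The SAP already reports what was observed ("missing data occurred only on items measuring social support"), so for data already analysed the ANCOVA must be labelled post hoc.

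Items 1 to 3 need no new data and no design change. Item 4 costs one error degree of freedom and, at 6-7 per arm, about 2-3 power points against the interaction if r is near 0.9. It gains about 4-5 points at r = 0.5, and about 10 points at r = 0.5 with an assumed 14 per arm.
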